6.0 Schema for Study

	Pre-Registration	Week 1	Week 2	Week 3	Week 4	Week 5	Week 6	Week 7	Week 8	Follow-Up (f)	At Relapse
History & PE, KPS	x	x ^e	x ^e	x ^e	x ^e	x ^e	x ^e	x ^e	x ^e	x	x
CBC, Differential, Platelets	x			x			x			x	x
SMA-12	x ^a										x
PET	x									x ^g	x
Chest X-Ray/Chest CT	x ^b									x ^g	x
Brain Scan (CT or MRI)	x ^b									x ^g	x
PFTs/EKG/Cardiac SPECT	x ^c									x ^c	
Toxicity Evaluation		x ^e	x ^e	x ^e	x ^e	x ^e	x ^e	x ^e	x ^e	x ^e	
Pregnancy Test	x ^d										
Biomarker Study	x ^h										
4DCT		x ^k	x ^k	x ^j	x ^j	x ^k	x ^k	x			
Radiation Therapy ^f		x	x	x	x	x	x	x	x		

- SMA-12 = serum creatinine, cholesterol, SGOT, glucose, Alk Phos, total bilirubin, total protein, albumin, uric acid, phos, calcium, BUN. SMA-12 is optional. CBC with differential, platelet count, electrolytes, BUN, creatinine within 30 days is required.
- Chest X-ray (optional), MRI or CT scans of Brain, PET or CT of chest are required within 3 months prior to radiotherapy.
- PFTs (FEV-1, FVC, and DLCO) and EKG should be obtained within three months prior to the initiation of XRT. Cardiac SPECT is recommended if lesion is close to heart and cardiac toxicity is of concern and/or when EKG is abnormal.
 Two Pulmonary function tests will be performed within first one year \pm 5 month after the completion of RT, then annually for two years. It is preferred that PFT is performed in the second and fourth follow up visit after completion of concurrent radiotherapy and chemotherapy, and then annually for two years. If no 6 week follow-up, then PFT is preferred to be performed in the first and third visit. EKG will be conducted in the third or fourth f/u visit and then annually for two years. If cardica toxicity is of concern based on treatment plan and/or abnormal EKG, cardiac SPECT should be performed in the third or fourth f/u visit and then as clinically indicated.
- Serum pregnancy test pre-study entry as applicable.
- PE including weight, performance status, vital signs. Radiation induced acute reactions including esophagitis, pneumonitis should be evaluated weekly.
- Follow-up is at 6 weeks after completion of radiotherapy, then every 3 months (+/-1 month) x 2 year, then every 6 months (+/- 1 month) x 3 years, then yearly. CBC with differential, platelet count, electrolytes, BUN, creatinine is recommended during the follow-up. Long term toxicity for esophagus and lung will be evaluated.
- Obtain chest CT if symptoms. If no symptoms, obtain chest CT in the second follow up after completion of radiotherapy and then every 3 months (+/-1 month) during years 1 and 2, then every 6 months (+/- 1 month) for three years and then annually. Brain scan is indicated if patient develops neurological symptoms. PET scan is required between 2-6 months after finishing treatment including chemotherapy if it is given. When PET is available, chest CT is not required. PET scan is required to evaluate recurrent disease.

- h. 10 ml of additional peripheral blood will be collected at the time of pre-registration blood work up. The blood sample will be frozen using a -80 degree centigrade refrigerator for future biomarker study.
- i. Radiotherapy need not start on a Monday but shall not start on a Friday.
- j. 4D-CT scanning will be performed at least in weeks 3 or 4 and 7
- k. 4DCTs in weeks 1, 2,5,and 6 are optional.

7.0 Radiation Therapy

7.1 Definition of Target Volumes

- GTV** Gross tumor volume is all known gross disease as demonstrated on end ventilation data set (30% phase as determined by Varian RPM or equivalent respiratory monitoring system) of the planning 4DCT using a lung window, and modified as deemed necessary based on PET/CT, diagnostic CT and other clinical studies.
- iGTV** The envelope of motion of the GTV constructed by any means but verified across all phases of the 4DCT dataset and the PET scan.
- CTV** Clinical target volume is the subclinical involvement around the GTV on the end ventilation dataset (30% phase as determined by Varian RPM or equivalent respiratory monitoring system). The CTV is estimated by an 8-mm isotropic expansion of the GTV to encompass microextensions of the tumor (CTV=GTV+8 mm). This should be edited by the attending based on clinical experience of disease spread.
- iCTV** Internal Clinical target volume is the envelope of motion of the CTV during In this study, The iCTV is estimated by an 8-mm isotropic expansion of the iGTV to encompass microextensions of the tumor (iCTV = iGTV+8mm); This should be edited by the attending based on clinical experience of disease spread.
- PTV** Planning target volume is iCTV plus a margin to ensure that the prescribed dose is actually delivered to the iCTV. For the purpose of reporting the PTV for proton treatment shall only include lateral uncertainties for each beam and not include any depth uncatinties (ICRU 78). The PTV shall be the iCTV expanded isotropically by 5 mm. This reporting sturtuce should not replace a beam-by-beam analysis of coverage using beam-specific PTV (see below).
- B-PTV** Beam specific PTV. For proton planning, each beam has an individual and unique PTV expansion from the iCTV. In the plane perpendicular to the proton beam axis, the PTV expansion from the iCTV is a fixed distance of 5 mm for setup uncertainites. However, along the direction parallel with the proton beam axis, the PTV expansion (distal and proximal margins) from the iCTV is based on the range uncertainty of the beam.

Treatment planning parameters, including distal and proximal margins, will be calculated based on published formulae, modified locally and adopted as standard of practice (Moyers et al, 2001; Engelsman et al, 2006; Kang et al,

2007).

PRV: Planning organ at risk volume (OAR) is used *to ensure with a high probability that adequate sparing of the OAR will actually be achieved* (ICRU 78) for this study OARs require PRVs will be identified in the planning constraints table.

7.2 Radiation Doses

7.2.1 The total radiation dose for the tumor target will be 87.5 Cobalt Gray Equivalent (CGE) at 2.5 CGE per fraction, once a day, 5 fractions per week. 100% of the iCTV should be covered by the prescribed dose. For proton treatments this will be achieved by ensuring that each beam covers the iCTV plus the margins for not only lateral but also range uncertainties (ICRU 78). Caution should be used as beams should not be modified based on a static evaluation.

7.2.2 Normalization of the treatment plan will cover 95% of the PTV with the prescription dose. The minimum PTV dose must not fall below 95% of the prescription dose. The PTV is assumed to be the beam-specific PTV.

7.2.3 Deviations from dose prescription for target volumes:

7.2.3.1 No deviation: $\geq 99\%$ of the PTV receives $\geq 95\%$ of the prescribed dose, and a contiguous volume of no more than 2 cc inside PTV exceeds 110% of the prescribed dose.

7.2.3.2 Minor deviation: Deviations of this magnitude are not desirable, but are acceptable. Coverage that is equal to 95% of the prescribed dose and falls between 99% and 95% of the PTV, or a contiguous volume of no more than 2 cc inside the PTV exceeds 120% of the prescribed dose. Similar considerations apply for each beam-specific PTV.

7.2.3.2 Major deviation: Coverage that is less than 95% of the prescribed dose and falls between 99% and 95% of the PTV, or a contiguous volume of greater than 2 cc inside the PTV exceeds 120% of the prescribed dose. Similar considerations apply for each beam-specific PTV.

7.2.4 Tolerance Limits for Critical Structures (2.5 CGE/Fraction)

Table 1: OAR Dose Limits

OAR	Label	Dose limit	Description
Normal Lung	Lung	20 CGE < 40% 10 CGE < 50% 5 CGE < 60% Mean Lung Dose (MLD) < 20 CGE	Normal lung - C contoured on ventilation dataset
Esophagus:	Esophagus	60 CGE < 50% 74 Gy < 10 cc Max Dose < 80 CGE	Esophagus contou on any dataset
Spinal Cord	Cord	Max Dose < 45 CGE	Spinal Canal
Spinal Cord PRV	Cord PRV (5 mm)	Max Dose < 60 CGE	Spinal Canal + 5 radial expansion
Brachial Plexus:	BP	Max Dose < 74 CGE 70 CGE < 10 cc	

Liver	Liver	30 CGE < 40%	
Kidney	Kidney	20 CGE < 50%	Both kidneys combined if both are functional
Functional Kidney	FunKidney	20 CGE < 25%	If only one kidney function, it should be contoured separately
Bronchial tree PRV	BroncPRV	87.5 CGE < 10 cc	Bronchial tree contoured down to tertiary bronchus on a lung window/level
Major vessels PRV	VesselPRV	87.5 CGE < 10 cc	See inclusion criteria
Heart-Atria	Atria	70 CGE < 10% 60 CGE < 15% 50 CGE < 20% 45 CGE < 30% 40 CGE < 40% 30 CGE < 50%	
Heart-Ventricles	Ventricles	70 CGE < 5% 60 CGE < 10% 50 CGE < 15% 45 CGE < 20% 40 CGE < 30% 30 CGE < 40%	

7.2.5 Major deviation: Doses outside the limits for OARs listed in table 1 will be considered major deviations and not acceptable.

7.2.6 Dose reporting: The digital dose distribution data to be reported includes the complete treatment plan. Its components include patient images on the mid ventilation dataset, contours of all structures, beam configurations and characteristics including beam shaping devices or scan patterns as appropriate, treatment couch parameters, dose distributions, dose volume histograms for target volumes and critical normal structures.

7.3 Simulation, Immobilization, Image-Guided Radiation Simulation

7.3.1. All simulations will be done on CT scanners capable of acquiring 4D CT image data sets. Only CT scanners and scanning protocols which have been calibrated specifically for proton calculations should be used.

7.3.2. Each patient will be positioned in an immobilization device in the treatment position on a flat table and imaged in treatment position.

7.3.3. The imaging session will consist of acquisition of a 4DCT covering the entire lungs as well as the entire treatment volume plus at least 5 cm. (Also see section 7.3.5.)

7.3.4. If the tumor is observed to move more than 1 cm on the 4DCT (edge to edge at motion extremes) or if critical normal tissue sparing is of concern, respiratory gated treatment, either free breathing or breathhold, should be considered.

7.3.5. An extended range free breathing scan may be acquired at the same time to serve as an anatomical reference and/or to look for distant metastasis.

7.3.6 Image-guided adaptation

- 7.3.6.1 All treatments must be done on treatment units with kilovoltage radiographic imaging.
- 7.3.6.2 In addition to the 4D CT simulation for planning of treatments, 4D-CT scanning will be performed at least in weeks 3 (or 4) and 7. Optionally, additional 4D CTs may be acquired in weeks 1, 2, 5 and 6.
- 7.3.6.3 The original CT will be fused with the weekly CT. The original contours will be transferred to the new CT and reviewed by the attending physician. If deemed necessary by him or her, new contours will be drawn and new dose distribution calculated using the original beam configuration. If the changes in DVHs derived from new dose distribution exceed the level of minor deviation of the target or normal tissue dose constraints, a new treatment plan will be designed for the remainder of the treatments.
- 7.3.6.4 Composite dose distribution received by each patient over the course of radiotherapy will be computed. Dose calculations will be performed for each of ten phases of the respiratory cycle for each of the CT scans acquired over the course of RT. They will be deformed to a reference phase (typically the end-exhale phase) and averaged. Such computations are necessary mainly to correlate dose distributions with response. They need to be performed only at the time of outcomes analyses.

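### The composite dose in 7.3.6.4 is a ten-phase average for every patient, so it is not the received dose in anyone treated gated or in breath-hold; minor, exploratory use only

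*Combined protocol and SAP*

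**What the plan says.** Section 7.3.6.4 states its aim for all patients: "Composite dose distribution received by each patient over the course of radiotherapy will be computed". The method follows: "Dose calculations will be performed for each of ten phases of the respiratory cycle for each of the CT scans acquired", then deformation to a reference phase (usually end-exhale) and averaging. No phase weights, beam-on window or exception by delivery technique are given. On purpose and timing it adds: "Such computations are necessary mainly to correlate dose distributions with response", and "They need to be performed only at the time of outcomes analyses".

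Three other places bear on this:

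- Section 7.3.4: if the tumour moves more than 1 cm, or sparing of critical normal tissue is a concern, "respiratory gated treatment, either free breathing or breathhold, should be considered". Section 7.4.2.1 requires suitable motion management above 1 cm without naming a technique.
- Section 7.3.6.2: "4D-CT scanning will be performed at least in weeks 3 (or 4) and 7". These repeat scans are 4DCT; no repeat breath-hold scan is described.
- Section 7.1 has the motion envelope of the gross tumour (iGTV) "verified across all phases of the 4DCT dataset and the PET scan", and 7.2.1 adds that "100% of the iCTV should be covered by the prescribed dose".

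**The concern.** An equal average over all ten phases describes a patient who breathes freely with the beam on throughout. A gated patient is irradiated in only some phases, and a breath-hold patient in a state that need not match any free-breathing phase. For both, the computed quantity is not what 7.3.6.4 calls it.

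What is at stake is the dose variable in a later exploratory analysis. The affected patients would not be a random subset: under 7.3.4 they are chosen for large motion or for normal-tissue concern. Any error would therefore be tied to tumour motion, in a trial of at most 40 patients. Patients treated ungated are not affected.

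**Working it through.** **Text.** The protocol gives no figure here to reproduce. Read side by side, 7.3.6.4 covers every patient and all ten phases, while 7.3.4 permits delivery in fewer phases or in breath-hold. Neither refers to the other, and 7.4.2 and 7.4.3 do not link them. Section 7.4.2.2 points to a separate physics document that is not supplied, but cites it for planning.

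**Weight given to beam-off phases.** If the beam is on in k of ten phases, an equal-weight average takes (10 − k)/10 of its weight from phases with the beam off: 80% for k = 2, 70% for k = 3, 50% for k = 5. The gate width k is an assumption.

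**What that does to dose: a one-dimensional illustration for gating.**

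Inputs from the protocol:
- CTV margin 8 mm and PTV margin 5 mm (7.1).
- Prescription 87.5 CGE (7.2.1).
- Dose at the PTV edge 95% of prescription, the minimum allowed in 7.2.2.
- Field covering the all-phase envelope (7.1, 7.2.1).

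Assumed inputs:
- Motion A of 10 mm (range 10 to 20).
- Gross tumour half-length 20 mm.
- Gaussian field edge with SD 5 mm (range 5 to 8).
- Gate of the three phases nearest end-exhale.

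Formulas, with distance along the motion axis in mm:
- Tissue offset in phase k: s_k = A·sin²(πk/10), k = 0 to 9; sin⁴ was also run.
- Static dose D(x): the difference of two normal distribution functions, one for each field edge.
- Rule in 7.3.6.4: mean of D(x + s_k) over all ten phases.
- Delivered: mean of D(x + s_k) over the three gate phases.
- Both are evaluated on tissue outside the CTV that moves with the tumour.

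Results for A = 10 mm, SD 5 mm, sin²:

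| Length above | Ten-phase average | Delivered in gate | Excess |
|---|---|---|---|
| 20 CGE | 45.8 mm | 43.9 mm | 45.8/43.9 − 1 = +4% |
| 10 CGE | 51.4 mm | 48.5 mm | 51.4/48.5 − 1 = +6% |
| 5 CGE | 55.8 mm | 52.3 mm | 55.8/52.3 − 1 = +7% |

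At the CTV edge, as a fraction of prescription, the ten-phase and delivered doses are 0.999 v 1.000 on the end-inhale side and 0.999 v 0.997 on the end-exhale side.

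Excess by motion, over both SDs and both waveforms:

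| Motion | 20 CGE | 10 CGE | 5 CGE |
|---|---|---|---|
| 10 mm | +2 to +5% | +3 to +6% | +3 to +7% |
| 15 mm | +4 to +9% | +6 to +12% | +7 to +13% |
| 20 mm | +7 to +14% | +9 to +17% | +10 to +19% |

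Over this grid the CTV-edge difference is at most 0.0067, under 0.7 percentage points. Varying the gate from one to five phases gives +1.7 to +13.5%, +2.4 to +17.3% and +2.7 to +18.7% for 20, 10 and 5 CGE, with a CTV-edge difference of at most 0.0091, so the pattern does not hinge on a three-phase gate. Tissue that does not move shows no difference. Breath-hold was not modelled.

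**Where the composite dose is used.** Section 9.0 tests 2-year local control and acute pneumonitis, and monitors grade 3+ pneumonitis; none of these uses a dose variable. Replanning under 7.3.6.3 rests on recalculated plan dose-volume histograms, not on the composite. Section 1.0 does not list a dose-response correlation among the goals.

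**The case against.** The strongest reply is that nothing of consequence depends on this. The stated use is correlation with response; if that means tumour response, the modelled effect is close to nil. No section states a correlation of composite dose with lung outcomes, although the word mainly in 7.3.6.4 leaves other uses open. Gating is only to be considered, so there may be no such patients. An analyst might also depart sensibly from the rule, or find guidance in the physics document that is not supplied. All of this stands, and it sets the severity. It does not remove the gap: 7.3.6.4 states its own rule for received dose without pointing elsewhere, and for a permitted technique the rule gives the wrong quantity.

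The model is also open to challenge. It sends a gated beam to a target covering all phases, which follows 7.1 and 7.2.1 literally, but gating may be used to allow a smaller field. It is one-dimensional and omits lung deformation, density change and proton range effects. That stands too.

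A reader might infer any of three stronger things:

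- *That tumour doses would be materially wrong.* This would need targets drawn for the gate alone, which the text does not describe.
- *That the lung volumes at 20, 10 and 5 CGE in Table 1 of 7.2.4 would be overstated by the percentages above.* Those are lengths outside the CTV along one axis; no organ volume was computed.
- *That mean lung dose is safe.* The model's mean-dose ratio of about 1.000 follows almost automatically from sliding a fixed profile along an unbounded line, so it is no evidence either way.

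**Conclusion.** The point holds at the lowest severity. For any patient treated gated or in breath-hold, the quantity defined in 7.3.6.4 is not the dose received. The number affected could be anything from 0 to 40, and the documents do not narrow it.

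With an all-phase target the tumour-dose error is negligible, and the discrepancy lies mainly in moving normal tissue within the dose fall-off. The order of size, 2 to 7% in length above 5 to 20 CGE at 10 mm motion and up to about 19% at 20 mm, rests on the assumed motion, tumour size, gate and field edge. It is an illustration, neither a typical value nor a bound.

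Only the exploratory use of composite dose at outcomes analysis is affected, chiefly if that dose is related to normal-tissue outcomes. The documents give no ground for extending this to local control, the pneumonitis comparison, the power statements, the stopping rule or replanning. The one reservation on the text is the physics document, which was not available to check.

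**What to change.** Add one or two sentences to 7.3.6.4:

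- **Ungated free breathing:** keep the ten-phase average.
- **Gated:** average only the phases inside the gate, weighted by each phase's share of beam-on time, using the per-phase calculations already required.
- **Breath-hold:** use breath-hold scans if any were acquired, at planning or later. The protocol requires only 4DCT, so where none exists, flag the composite dose as approximate.

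Record delivery technique and gate window for each patient, preferably during treatment, since they may be hard to recover later.

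The cost is two recorded fields per patient and slightly more analysis work. No extra scan and no change to treatment is needed, and the computation is due only at outcomes analysis.

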7.4 Treatment Planning

7.4.1 Critical structures

- 7.4.1.1 All OARs listed in the section 4.0 and likely to receive more than 50% of their tolerance doses shall be contoured.
- 7.4.1.2 The tolerance doses to various organs are provided in Table 1.

7.4.2 Motion Management

- 7.4.2.1 All patients on this protocol will undergo a 4D CT for treatment planning. Tumors that are found to move more than 1 cm will be treated with appropriate motion management.
- 7.4.2.2 Planning shall be done in accordance with the P01 physics document.

7.4.3 Dose calculation

- 7.4.3.1 Doses are to be calculated with CT based heterogeneity correction, i.e., correction is to be made for density differences between air spaces, lung, water-density or bony tissue.
- 7.4.3.2 Treatment planning should be performed in accordance with the prescribed doses to each target, together with restrictions in dose to normal tissues
- 7.4.3.3 The average intensity projection (AveIP) derived from the 4DCT set should be used as a reference scan for dose calculation.

7.5 Patient Registration

- 7.5.1 Patients should be registered as required by either MGH or MDACC institutionally

mandated systems. At MGH, the Quality Assurance for Clinical Trials office defines the required registrations. At MDACC, CORE, the Clinical Oncology Research System is used.

- 7.5.2 Patient data will be entered onto TrialDB, independent of which institution the patient originates from. This registration must be disclosed as part of the informed consent.

The delivered treatment dose distribution, with structures and DVH, will be sent to the ITC at Washington University in St. Louis. This should be disclosed as part of the informed consent. The ITC will provide digital data integrity quality assurance (DDIQA), which will facilitate the review of delineation and dosimetry of GTV, CTV, PTV, and designated organs at risk (critical structures) on all cases. Detailed instructions for submitting digital data to the ITC may be found on the ATC web site <http://atc.wustl.edu/>

7.6 Radiation Therapy Quality Assurances

- 7.6.1. All contours and treatment plans will be peer reviewed, following the normal practice of the institution which enrolls the patient. Contours will be reviewed by the physician co-PI of the protocol or his/her designee

- 7.6.2 Plans will be reviewed by the physician co-PI and physics co-PI of the protocol or his/her designee for compliance with the protocol.

- 7.6.3 Plan review for the patients from one institution by the staff of the other institution will utilize the resources of the Image-Guided Therapy QA Center (ITC) at Washington University, St. Louis.

8.0 Chemotherapy

Adjuvant Chemotherapy 4 weeks after RT would be allowed at the discretion of the treating physicians.

9.0 Statistics

The local control rate at 2 years is 50% with historical photon data. We anticipate that proton therapy will increase the local control rate to 75%. With a sample of 40 patients we will have 93% power to detect an increase in the local control rate at 2 years from 50% to 75% with a 1-sided significance level of 5%. This calculation assumes that we will accrue 20 patients per year for 2 years and that we will follow all patients for 2 years. We will estimate the local control rate at 2 years with a 95% confidence interval using the Kaplan-Meier product-limit estimator.

With current photon therapy using similar relative biological effectiveness (RBE) the rate of grade 3 acute pneumonitis is less than 15%, and the chronic pneumonitis rate is 15%. With a sample of 40 patients we will have 81% power to detect a decrease in the rate of grade 3 acute pneumonitis from 15% to 3.75% with a 1-sided significance level of 5%. We will estimate the

grade 4 acute pneumonitis rate with an exact binomial 95% confidence interval.

We will enroll and evaluate a maximum of 40 patients at a rate of 20 patients per year. We will monitor the rate of grade 3+ pneumonitis, which is assessed within 3 months following completion of therapy. Our target grade 3+ pneumonitis rate is 10% or less, based on RTOG Study 9311. We assume a beta(0.2, 1.8) prior distribution for this toxicity rate. This prior distribution has a mean of 10% and a standard deviation of 17%.

We will stop the trial early if $P(\text{grade 3+ pneumonitis} > 10\% \mid \text{data from the trial}) > 0.925$. That is, given the outcomes from the patients who have already been evaluated, if we determine that there is more than a 92.5% chance that the grade 3+ pneumonitis rate is more than 10% we will stop the trial. This decision rule gives the following stopping rule. Stop the trial if

$$\begin{aligned}
 & [\# \text{ of pts with grade 3+ pneumonitis} / \# \text{ of pts evaluated}] \\
 & \geq 4/15, 5/17, 6/24, 7/31, 8/38
 \end{aligned}$$

The operating characteristics of this monitoring rule are shown in Table 1.

Grade 3+ Pneumonitis Rate	Probability of Stopping Early	Sample Size		
		P ₂₅	P ₅₀	P ₇₅
0.050	0.012	40	40	40
0.075	0.053	40	40	40
0.100	0.131	40	40	40
0.150	0.413	21	40	40
0.200	0.709	15	22	40
0.250	0.895	15	15	25
0.300	0.970	15	15	16

Once we have completed the study we will estimate the grade 3+ pneumonitis rate with a 90% credible interval. If we have grade 3+ pneumonitis in 4 of the 40 patients (10%), then our 90% credible interval for the grade 3+ pneumonitis rate will be 3.7% to 18.5%. If we have grade 3+ pneumonitis in 2 of the 40 patients (5%), then our 90% credible interval for the grade 3+ pneumonitis rate will be 1.1% to 11.8%.

In addition, if there is any grade 4 or 5 toxicity directly caused by proton therapy, the trial will be re-evaluated and decision will be made about modification of treatment or stopping the trial.

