1.0 Objectives

To assess the therapeutic efficacy and toxicities of proton radiotherapy with escalated/accelerated dose for patients with inoperable centrally/superiorly located stage Ia (T1, N0, M0), any stage Ib (T2, N0M0) and selected stage II (T3N0M0) non-small cell lung cancer (NSCLC).

Primary goals:

1. Improve the 2 year local control rate at the primary site over historical results
2. Reduce acute and chronic toxicity (according to the NCI Common Terminology Criteria for Adverse Events version 3.0 [CTCAE v3.0])

Secondary goals:

1. Improve the disease specific survival rate at 2 years over historical results.
2. Study the potential of pre- and post treatment PET/CT in predicting clinical outcome.
3. Study the role of biomarkers in predicting therapeutic response and toxicities.

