2. A dose-response relationship for disease-free survival in stage I NSCLC has been reported. Dosoretz et al showed that actuarial disease-free survival at 2-years was 50%, 33%, 22%, and < 20% with 70 Gy (n=4), 60-69 Gy (n=116), 50-59 Gy (n=26), and < 50 Gy (n=6), respectively. The actuarial risk for local failure at 3 years was 33%, 60% and 58% for > 70 Gy (n=4), 60-69 Gy (n=91) and 50-59 Gy (n= 19), respectively.
3. The preliminary data from the RTOG 9311 (Bradley et al) phase I dose escalation study showed that acute toxicity rates were acceptable for dose up to 90.3 Gy (less than 15% grade ≥ 3 pneumonitis and no esophagitis). However, late toxicities were more pronounced. Late grade ≥ 3 radiation pneumonitis occurred at a rate of 15% for patients with a V20<25% for patients treated to dose levels of 77.4 Gy or above with fraction size of 2.15 Gy. For patients with a V20 of 25-37%, late grade ≥ 3 pneumonitis occurred at the rate of 15% for the doses of 70.9 Gy or above. Late grade ≥ 3 esophagitis occurred in less than 7% of patients. The rate of late esophagitis was not directly correlated with dose, but it may be related to the volume of the esophagus treated.

Data in support of proton therapy in early stage NSCLC:

1. Shioyama reported the clinical outcome of 28 patients with stage I NSCLC treated with proton radiotherapy to the median fraction of 3 Cobalt Gray Equivalent (CGE) (range 2-6 CGE) and to a median total dose of 76 CGE (range 49-93 CGE). The 5-year overall survival rate was 70% with local control of 89% for stage IA. However, for stage IB, the local control was 39% and the 5-year overall survival was 15%. Only one case of grade 3 acute toxicity and little late toxicity was observed. In this study, the clinical outcome for stage IA patients was comparable to surgical resection. However, for stage IB patients, the result was much worse than surgical resection and 21% patients recurred in the mediastinum. Since PET scanning was not used for clinical staging, it is possible that the group of patients with stage IB was understaged and significant tumor volume was missed.

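### The only powered toxicity comparison tests acute pneumonitis against 15%, which the plan gives as the chronic photon rate and only as an upper bound for the acute rate

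*Combined protocol and SAP*

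**What the plan says.** Section 1.0 makes toxicity the second primary goal: "Reduce acute and chronic toxicity (according to the NCI Common Terminology Criteria for Adverse Events version 3.0".

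Section 9.0 gives the photon background: "the rate of grade 3 acute pneumonitis is less than 15%, and the chronic pneumonitis rate is 15" per cent. It then states that 40 patients give "81% power to detect a decrease in the rate of grade 3 acute pneumonitis from 15% to 3.75" per cent, at a one-sided 5% level. No rejection rule is printed.

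Section 2.0 makes the same split for the photon dose-escalation trial, RTOG 9311. Acute toxicity was "acceptable for dose up to 90.3 Gy (less than 15% grade ≥ 3 pneumonitis and no esophagitis). However, late toxicities were more pronounced". For the late rate it says "Late grade ≥ 3 radiation pneumonitis occurred at a rate of 15% for patients with a V20<25" per cent at 77.4 Gy or above, and it gives 15% again for V20 of 25-37% at 70.9 Gy or above.

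The other pneumonitis items in Section 9.0 are:
- an exact 95% interval for grade 4 acute pneumonitis;
- a Bayesian stopping rule on early grade 3+ events, whose safety ceiling is worded as "Our target grade 3+ pneumonitis rate is 10% or less, based on RTOG Study 9311", and whose observation window ends 3 months after treatment;
- a closing estimate ("Once we have completed the study we will estimate the grade 3+ pneumonitis rate with a 90% credible interval").

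None of these compares protons with a photon rate.

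**The concern.** In a single-arm test for a reduction, a null set too high favors the new treatment. Rejecting 15% shows that the proton acute rate is below 15%. By the protocol's own account, that is already true of photons. A result could therefore meet the powered criterion with no improvement in acute pneumonitis.

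The criterion supports the acute half of a primary goal, and it is the only toxicity comparison with a stated power. The figure of 15% does describe late pneumonitis, which Section 2.0 presents as the more serious photon problem, yet Section 9.0 sets no estimate or interval labelled as chronic beside it.

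**Working it through.** **Inputs.** From Section 9.0: n = 40, null 15%, alternative 3.75%, one-sided 5%, stated power 81%; photon acute rate below 15%, chronic rate 15%. Section 9.0 writes grade 3 and Section 2.0 writes grade 3 or higher; I treat these as the same endpoint. The photon acute rates of 14%, 12%, 10% and 7.5% used below are assumptions.

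**Formula.** P(X ≤ c | p) = Σ C(40, x) pˣ (1 − p)^(40−x), summed over x = 0 to c. The rule is the largest c with P(X ≤ c | null) ≤ 0.05.

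**Step 1: reproduce the plan's figure.**
- Null 15%: P(X ≤ 2) = 0.0015 + 0.0106 + 0.0365 = 0.0486, and P(X ≤ 3) = 0.130. So c = 2.
- Power at 3.75%: P(X ≤ 2) = 0.2168 + 0.3378 + 0.2567 = 0.811.

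This matches the stated 81%, so the implied rule is at most 2 events in 40. The stopping rule does not disturb these figures, because each of its boundaries needs at least 4 events.

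**Step 2: chance of meeting that rule when protons equal photons.** At 10%, for example: 0.9⁴⁰ + 40(0.1)(0.9³⁹) + 780(0.01)(0.9³⁸) = 0.0148 + 0.0657 + 0.1423 = 0.2228.

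**Step 3: reset the rule to hold one-sided 5% at n = 40, and recompute the power at 3.75%.**

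| Photon acute rate | P(X ≤ 2), no change | Cut-off holding 5% | Exact size | Power at 3.75% |
|---|---|---|---|---|
| 15% (plan) | 4.9% | ≤ 2/40 | 0.049 | 81% |
| 14% | 6.8% | ≤ 1/40 | 0.018 | 55% |
| 12% | 12.6% | ≤ 1/40 | 0.039 | 55% |
| 10% | 22.3% | 0/40 | 0.015 | 22% |
| 7.5% | 41.4% | 0/40 | 0.044 | 22% |

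At 7% or lower no outcome in 40 patients rejects at 5%, since even 0/40 is too likely under the null.

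**Step 4: size needed.** For 10% against 3.75%, exact power first reaches 80% at 103 patients (cut-off ≤ 5, power 0.81).

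**Step 5: the plan's own example.** Section 9.0 illustrates 2 events in 40. Against 15% the one-sided p is 0.049; against 10% it would be 0.22. The plan's 90% credible interval for that result, 1.1% to 11.8%, excludes 15% but not 10%.

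**The case against.** The plan states a power, not a decision. The cut-off of 2 in 40 is derived, and the closing analysis it specifies for grade 3+ pneumonitis is a credible interval that would show a reader what is and is not excluded. This stands: one cannot say that the plan will declare a false reduction at some fixed rate. A stated power at a stated significance level still presupposes a test, and this one has the wrong null.

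The size is also uncertain. If the photon acute rate were just under 15%, the excess would be small (6.8% at 14%), and the documents cannot rule that out. The summary in Section 2.0 gives 15% for grade 3 or higher pneumonitis at 90.3 Gy, the schedule the protocol calls equivalent to its own. But that figure carries no acute or late label, and Section 9.0 and the RTOG 9311 description in Section 2.0 both put the acute rate below 15%. It does not rescue the null.

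A reader might infer three stronger points that the documents do not support.

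- *That the error is 22%.* This needs a photon acute rate of 10%, which the documents do not state. The 10% in Section 9.0 is a safety target for the proton trial. For the same reason, 10% and 15% are not two conflicting photon benchmarks: a stopping ceiling and a historical comparator serve different purposes.
- *That chronic toxicity is ignored.* Section 5.2 commits to analyzing chronic grade 3 or higher toxicity, Section 6.0 to evaluating long-term lung and esophageal toxicity, and Section 2.0 to comparing toxicities with photon data.
- *That chronic pneumonitis should be formally tested against 15%.* With death counted as a competing event, deaths make such a test easier to pass. Suppose 20% die before any late event (an assumption; Section 2.0 reports 3 of 15 dead at a median of 16.5 months in the preliminary series). A 15% rate becomes 0.8 × 15% = 12%, and at most 2/40 is then met 12.6% of the time. How the historical 15% was estimated is not stated. It also comes from particular V20 and dose subgroups, while Section 7.2.4 allows lung V20 up to 40%.

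**Conclusion.** The point holds. The null in the only powered toxicity comparison is an upper bound on the photon acute rate and equals the rate given for chronic pneumonitis. The direction is certain: any true photon acute rate below 15% makes the implied rule easier to meet without benefit than its size of 0.049 suggests. The magnitude is not known from the documents. It runs from 6.8% at 14% through 12.6% at 12% to 22.3% at 10%, all assumed rates. The stated 81% power is correct arithmetic for 15%; it falls to about 55% for nulls of 12% to 14% and about 22% for 7.5% to 10%. These figures assume an exact binomial test on all 40 patients. Safety monitoring is not affected.

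**What to change.** In Section 9.0:

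1. Replace 15% with the point estimate of the photon acute grade 3+ pneumonitis rate from the historical series, state its source, print the cut-off, and restate the power at n = 40.
2. If no point estimate can be obtained, delete the power sentence. Report the grade 3+ rate assessed within 3 months with an exact 95% confidence interval, and state that no reduction against photons will be claimed from it.
3. Report chronic grade 3+ pneumonitis, defined as onset more than 3 months after radiotherapy, separately with a 95% confidence interval. Set it beside the historical 15% without a formal test, and note that the 15% comes from particular V20 and dose subgroups.

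The cost is wording, one figure from the historical series, and an onset date for each grade 3+ lung event at visits where toxicity is already evaluated. The stopping rule and sample size do not change. The downside is that with 40 patients the trial may be unable to claim lower acute pneumonitis.
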